12.3.10 Interim analysis

No interim analysis is planned.

12.3.11 Analysis of data up to Week 32

To support submission for marketing approval, a 32-week analysis will be performed on data up to Week 32. All analyses pertaining to efficacy endpoints will be final in this 32-week

Trial ID: LP0162-1339	Date: 29-Aug-2018	Version: 4.0
		Page 102 of 129

analysis and will be included in a CTR in the original submission. No adjustments in significance level of the primary and secondary analyses will therefore be applied. Blinding of investigators and other site staff involved in the conduct of the trial will be maintained for the entire duration of the trial (please refer to Section 9.2.1 for further details).

The safety results for the safety follow-up period (Week 32 to 46) for all subjects will be included in an addendum to the original CTR and will be submitted as part of the 120-Day Safety Update.

12.3.12 General principles

Unless otherwise stated, all significance tests will be two-sided using the 5% significance level. All CIs will be presented with 95% degree of confidence.

An observed-cases approach will be used for tabulations of data by visit (i.e. involving only those subjects who attended each specific visit).

Categorical data will be summarised using the number and percentage of subjects in each category and treatment group. Continuous data will be summarised using the mean, median, standard deviation, minimum and maximum values.

All the analyses specified in the protocol will be reviewed in relation to the blinded data actually obtained and the statistical analysis plan update will be finalised before breaking the randomisation code.

Any changes from the statistical analysis planned in this clinical trial protocol will be described and justified in a protocol amendment, the statistical analysis plan update and/or in the CTR dependent on the type of deviation.

Appendix 1: Definitions of adverse events and serious adverse events

Adverse event definition

An AE is defined as any untoward medical occurrence in a patient or clinical investigation subject administered a pharmaceutical product and which does not necessarily have a causal relationship with this treatment. An AE can therefore be any unfavourable and unintended sign (including an abnormal laboratory finding), symptom, or disease temporally associated with the use of a medicinal (investigational) product, whether or not related to the medicinal (investigational) product. (ICH Harmonized Tripartite Guideline for GCP, E6 [R1]).

This definition includes:

- Accidental injuries.
- Events related to trial procedures.
- Reasons for any unfavourable and unplanned change in medication (drug and/or dose).
- Clinically significant worsening of pre-existing conditions.
- Reasons for admission to hospital or surgical procedures unless these were planned before enrolment.

It also includes AEs commonly observed and AEs anticipated based on the pharmacological effect of the IMP. In addition, any laboratory abnormality assessed as clinically significant by the investigator must be recorded as an AE.

Serious adverse event definition

An SAE is any untoward medical occurrence that:

- results in death.
- is life-threatening.
- requires inpatient hospitalisation or prolongation of existing hospitalisation.
 Planned hospitalisation or planned prolonged hospitalisation do not fulfil the criteria for being an SAE but should be documented in the subject's medical record.
- results in persistent or significant disability/incapacity.
- is a congenital anomaly/birth defect.

or

Trial ID: LP0162-1339	Date: 29-Aug-2018	Version: 4.0
		Page 108 of 129

• is a medically important condition. Events that may not be immediately life-threatening or result in death or hospitalisation but may jeopardise the subject or may require intervention to prevent one of the other outcomes listed in the definition above. Examples are intensive treatment in an emergency room or at home for allergic bronchospasm, blood dyscrasias and convulsions that do not result in hospitalisation, development of drug dependency or drug abuse.

Trial ID: LP0162-1339	Date: 29-Aug-2018	Version: 4.0
		Page 109 of 129

Appendix 2: Classification of adverse events

Severity

The *severity* of the AE should be described in terms of mild, moderate or severe according to the investigator's clinical judgement.

Mild	An AE that is usually transient and may require only minimal treatment or therapeutic intervention. The event does not generally interfere with usual activities of daily living.
Moderate	An AE that is usually alleviated with additional specific therapeutic intervention. The event interferes with usual activities of daily living, causing discomfort but poses no significant or permanent risk of harm to the subject.
Severe	An AE that interrupts usual activities of daily living, or significantly affects clinical status, or may require intensive therapeutic intervention.

If the severity of an AE worsens, a new AE should be recorded.

Causality

The *causal relation* of the AE to the use of the IMP should be described in terms of probable, possible or not related according to the following:

Probably related	Follows a reasonable temporal sequence from administration of the IMP. Could not be reasonably explained by the subject's clinical state, environmental or toxic factors or other therapies administered to the subject. Follows a known pattern of response to the IMP. Disappears or decreases on cessation or reduction in dose of the IMP. Reappears or worsens upon re-challenge.
Possibly related	Follows a reasonable temporal sequence from the administration of the IMP. Could also be reasonably explained by the subject's clinical state, environmental or toxic factors or other therapies administered to the subject. Follows a known pattern of response to the IMP.

Trial ID: LP0162-1339	Date: 29-Aug-2018	Version: 4.0
		Page 110 of 129

Not related	Does not follow a reasonable temporal sequence from administration of the IMP.
	Is better explained by other factors like the subject's clinical state, environmental or toxic factors or other therapies administered to the subject.
	Does not reappear or worsen upon re-challenge.
	Does not follow a known pattern of response to the IMP.

Similarly, the causal relationship to the use of NIMP (TCS) should also be evaluated using the same definitions as for the IMP (i.e. probably, possibly, or not related to NIMP).

Outcome

The *outcome* of the event should be classified and handled as follows:

Recovered/ resolved	The event has stopped. The stop date of the event must be recorded.
Recovering/ resolving	The subject is clearly recovering from an event. The event is not yet completely resolved.
Not recovered/not resolved	Event is still ongoing.
Recovered/re solved with sequelae	The event has reached a state where no further changes are expected and the residual symptoms are assumed to persist. An example is hemiparesis after stroke.
	The stop date of the event must be recorded. In case of a SAE, the sequelae should be specified.
Fatal	The subject has died as a consequence of the event. Date of death is recorded as stop date for the AE.
Unknown	Unknown to investigator, e.g. subject lost to follow-up.

Trial ID: LP0162-1339	Date: 29-Aug-2018	Version: 4.0
		Page 111 of 129

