11.3.2 LEO reporting responsibilities

Global Pharmacovigilance, LEO is responsible for assessing whether or not an SAE is expected. The relevant reference document for this clinical trial is:

For the IMP, the Investigator's Brochure, edition 16 and subsequent updates must be used.

For the NIMP (mometasone furoate, 0.1% cream) the latest version of the approved label must be used.

Global Pharmacovigilance, LEO will notify the regulatory authorities and concerned investigators of SAEs according to the current applicable legislation for the concerned countries.

The IRB(s)/IEC(s) will be notified of SAEs according to the current applicable legislation for the concerned countries.

Trial ID: LP0162-1339	Date: 29-Aug-2018	Version: 4.0
		Page 79 of 129

For all countries except the US, all SAEs which are assessed as causally related to the IMP(s) by either the investigator or LEO (ICH E2A Guideline), and which are unexpected (Suspected, Unexpected Serious Adverse Reactions [SUSARs]), are subject to expedited reporting to regulatory authorities and IRB(s)/IEC(s) according to the current applicable legislation in the concerned countries. Investigators will be notified of such SUSARs and the evolving safety profile on an ongoing basis.

For the US, as per Guidance for Industry and Investigators - Safety Reporting Requirements for INDs and BA/BE Studies, only those events for which the sponsor determines there is a reasonable possibility of a causal relationship are subject to IND Safety Reporting. Investigators will be notified of the evolving safety profile on an ongoing basis.

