12.3.9.1 Adverse events

To assess the safety of tralokinumab in combination with TCS when used to treat moderate-to-severe AD for 32 weeks, the frequency of AEs and SAEs are included as additional secondary endpoints.

AEs will be coded during the course of the trial according to Medical Dictionary for Regulatory Activities (MedDRA). AEs will be presented by preferred terms and primary system organ class (SOC).

Treatment-emergent AEs will be summarised, however, all AEs recorded during the course of the trial will be included in the subject data listings. An event will be considered treatment-emergent if started after the first use of IMP or if started before the first use of IMP (applicable if subject had a wash-out) and worsened in severity thereafter. The tabulations described in the following will only include the treatment-emergent events. In each of the tabulations, AEs will be defined by MedDRA preferred terms within primary SOC.

An overall summary of the number of treatment-emergent AEs and the number (percentage) of subjects with any treatment-emergent AEs, deaths, SAEs, premature discontinuations from the trial due to AEs, treatment-related AEs and severe AEs will be presented.

The number of AEs and the number of subjects experiencing each type of AE will be tabulated by treatment group. The percentage of subjects with AEs in the initial treatment period will be compared between treatment groups by a chi-square test or Fisher's exact test (if expected cell count <5).

Trial ID: LP0162-1339	Date: 29-Aug-2018	Version: 4.0
		Page 100 of 129

The severity for each type of AE will be tabulated by treatment group.

The causal relationship to IMP and NIMP (TCS) for each type of AE will be tabulated by treatment group.

Related AEs are defined as AEs for which the investigator has not described the causal relationship to IMP as 'not related'. The number of related AEs and the number of subjects experiencing each type of related AE will be tabulated. The percentage of subjects with related AEs in the initial treatment period will be compared between treatment groups by a chi-square test or Fisher's exact test (if expected cell count <5).

SAEs and AESIs will be evaluated separately. A narrative for each SAE will be given. AESIs and AEs leading to withdrawal from trial or permanent discontinuation of IMP will be tabulated and listed.

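### Appendix 2 makes fit with a known response pattern a feature of both related categories and its absence a feature of 'not related', which biases investigator causality against novel reactions

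*Protocol*

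**What the plan says.** Section 11.2 of the protocol makes the Appendix 2 definitions mandatory for classifying every AE. Appendix 2 offers three causality levels: the relation "should be described in terms of probable, possible or not related according to the following".

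- 'Probably related' has five features. The third and fourth read "Follows a known pattern of response to the IMP. Disappears or decreases on cessation or reduction in dose of the IMP".
- 'Possibly related' has three features. The second says that another reasonable explanation exists. The end of the second and the whole of the third read "other therapies administered to the subject. Follows a known pattern of response to the IMP".
- 'Not related' has four features. The first is "Does not follow a reasonable temporal sequence from administration of the IMP". The last is that the event does not "follow a known pattern of response to the IMP".

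The appendix does not say whether a category needs all of its features or whether they are indicators to be weighed. The same definitions apply to the NIMP (the topical corticosteroid).

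Two other sections rely on the result. Section 12.3.9.1 states: "Related AEs are defined as AEs for which the investigator has not described the causal relationship to IMP as 'not related". It tabulates these events and compares the arms on them in the initial treatment period. Outside the US, Section 11.3.2 makes the following subject to expedited reporting: "all SAEs which are assessed as causally related to the IMP(s) by either the investigator or LEO (ICH E2A Guideline), and which are unexpected". In addition, Section 11.6 limits follow-up of non-serious AEs after a subject leaves the trial to those rated possible or probable, for 2 weeks or until final outcome, whichever comes first.

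**The concern.** Whether an event resembles what is already known of the drug and whether the drug caused it are separate questions. Appendix 2 merges them. A novel reaction counts against itself because it is novel, and no related category is free of that feature.

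This sits badly with Section 11.3.2, which looks for events that are both related and unexpected. An investigator applying Appendix 2 is told that departure from the known pattern points away from related, while the reporting rule needs both properties together.

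At stake are the outputs and actions that rest on the investigator's rating. They become less sensitive for newly emerging harms, which a phase 3 safety assessment should be able to show. Investigators are blinded, so the pull acts in both arms. A new reaction to tralokinumab would arise only under tralokinumab, however, so the related-AE difference between arms would tend to be understated.

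**Working it through.** No arithmetic applies, because the point depends on no rate, alpha or sample size. The check sets one test event against the three definitions and then follows it through the rules that use the rating.

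**Test event:** timing reasonable, no other explanation found, no known pattern, no re-challenge done.

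| Feature | Probably | Possibly | Not related | Test event |
|---|---|---|---|---|
| Timing | reasonable | reasonable | not reasonable | reasonable |
| Other explanation | none reasonable | one is reasonable | one is better | none found |
| Known pattern | yes | yes | no | no |
| De-challenge | improves | not listed | not listed | may be unknown |
| Re-challenge | recurs | not listed | does not recur | not done |

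**Reading A, all features required.** The event fails 'probably' on pattern (and on re-challenge). It fails 'possibly' on pattern and because no alternative explanation exists. It fails 'not related' on timing and on explanation. No category fits, and Appendix 2 offers no fourth level.

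**Reading B, features indicative.** The event meets 2 of 5 features of 'probably' (timing, no other explanation), 1 of 3 of 'possibly' (timing) and 1 of 4 of 'not related' (pattern). The pattern feature counts against both related levels and is the only one that counts for 'not related'. The text therefore disfavours a related rating without forcing the opposite one.

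**Consequences if the investigator records 'not related':**

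| Rule | Whose causality rating | Effect |
|---|---|---|
| Related-AE table and chi-square or Fisher test (12.3.9.1) | investigator only; no sponsor override stated | event leaves the analysis |
| SUSAR outside the US (11.3.2) | investigator or sponsor | investigator's route lost, sponsor's route remains |
| Expedited reporting in the US (11.3.2) | sponsor only | no direct effect |
| Post-trial follow-up of non-serious AEs (11.6) | possible or probable rating | up to 2 weeks of follow-up lost |
| All-AE comparison and tables (12.3.9.1) | none | unaffected |
| AESI tabulation and listing (12.3.9.1) | none | unaffected |
| SAE report to the sponsor within 24 hours (11.3.1) | none needed to trigger it | unaffected |

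**The same event after the change proposed below.** Without the pattern feature, the event meets none of the remaining three features of 'not related': timing is reasonable, nothing explains it better, and re-challenge was not done. The reasonable-possibility floor places it in 'possibly related' or higher.

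**The case against.** The best defence is that the lists can only be indicative. If every feature were required, 'probably' would need a positive re-challenge and 'not related' a negative one, so many events could never be rated. This is persuasive, but Appendix 2 does not say so and Section 11.2 makes the definitions binding. Even on the indicative reading, the pattern feature still pulls against a novel event.

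A second defence is that the main safety evidence does not rest on causality. The endpoint is AE and SAE frequency by preferred term, all treatment-emergent AEs are tabulated and compared, all AEs are followed during the trial, and SAEs are followed to final outcome beyond it. This stands, and it limits the damage to the outputs listed in the working.

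Several stronger readings are tempting, but the documents do not support them:

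- **A novel serious reaction falls outside the SUSAR rule.** It does not. Outside the US the sponsor's rating alone is enough, in the US only the sponsor's counts, and every SAE reaches the sponsor within 24 hours.
- **No novel reaction can be rated related, so detection is nil.** On the strict reading the event is unclassifiable, which is not the same as 'not related'. Section 12.3.9.1 counts as related anything not so described. On the indicative reading the loss is partial.
- **Unexpected means no known pattern by definition.** The protocol does not define the pattern, and expectedness is a separate judgement made by the sponsor's pharmacovigilance group against the Investigator's Brochure. The two are likely to overlap, but nothing equates them.
- **The sponsor has no other causality standard.** Section 11.3.2 gives one for the US, a reasonable possibility of a causal relationship, and cites ICH E2A for other countries.
- **An excess of conjunctivitis, keratitis or eczema herpeticum would be hidden.** These are AESIs, tabulated and listed whatever their rating. Only their share of the related-AE outputs could be understated.
- **Permanent discontinuation under Section 9.7.1 rules out re-challenge and so worsens the problem.** Re-challenge can only help separate 'probably' from 'possibly', and Sections 11.6 and 12.3.9.1 treat those alike.

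**Conclusion.** The point holds as a flaw in the causality definitions with limited consequences. On either reading, Appendix 2 works against rating a novel reaction as related: it leaves the reaction without a category or tilts it away from the related ones.

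Three things are affected. The related-AE table and test can be understated with no stated back-up. The investigator's route to a SUSAR outside the US is weakened, with the sponsor's assessment as back-up. Novel non-serious events can miss up to 2 weeks of post-trial follow-up.

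The size cannot be stated. It depends on how often reactions outside the known pattern occur and how literally investigators read the list, and the protocol gives neither. The conclusion assumes that investigators apply Appendix 2 as written and that no other instruction overrides it. The Investigator's Brochure and the eCRF completion guidance are not available, so it cannot be judged which events would count as outside the known pattern. A later analysis plan would not cure this, because the rating is made at site under the protocol.

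The change should be made, as a correction of wording. It does not call the main safety comparisons into question.

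**What to change.** In Appendix 2:

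1. Delete the known-pattern feature from 'possibly related' and its negation from 'not related'.
2. State that an event with reasonable timing and a reasonable possibility of a causal link is at least 'possibly related', whether or not it is a known reaction. This matches the standard already used in Section 11.3.2 for the US.
3. State that the remaining features are indicative and need not all be met.
4. Apply the same wording to the NIMP assessment.

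Then check that Sections 11.3.2, 11.6 and 12.3.9.1 read consistently with the revised definitions. The work is a protocol text change and matching eCRF completion guidance. The downside is somewhat more AEs coded 'possibly related' and possibly more SUSAR reports.

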Appendix 3: Trial governance considerations

Appendix 3A: Regulatory and ethical considerations

This trial will be conducted in accordance with the protocol and with the following:

- Consensus ethical principles derived from international guidelines including the current version of the Declaration of Helsinki and Council for International Organizations of Medical Sciences (CIOMS) International Ethical Guidelines.
- Current version of applicable ICH GCP Guidelines.
- Applicable laws and regulations.

The appropriate regulatory authority(ies) must be notified of/approve the clinical trial as required.

The protocol, protocol amendments, subject information leaflet including the informed consent form (ICF), Investigator's Brochure, and other relevant documents (for example advertisements) must be submitted to an IRB/IEC by the investigator (in collaboration with LEO, if applicable) and reviewed and approved by the IRB/IEC prior to enrolment of subjects.

Any amendments to the protocol must be approved by/receive favourable opinion from relevant regulatory authorities and IRBs/IECs as required prior to the implementation.

The investigator will be responsible for the following:

- Providing written summaries of the status of the trial to the IRB/IEC annually or more frequently in accordance with the requirements, policies, and procedures established by the IRB/IEC.
- Notifying the local IRB/IEC of SAEs or other significant safety findings as required by IRB/IEC procedures.
- Providing oversight of the conduct of the trial at the trial site and adherence to applicable national and international legislation.

Appendix 3B: Informed consent process

Subjects shall receive written and verbal information concerning the clinical trial. This information will emphasise that participation in the clinical trial is voluntary and that the subject may withdraw from the clinical trial at any time and for any reason. All subjects will

Trial ID: LP0162-1339	Date: 29-Aug-2018	Version: 4.0
		Page 112 of 129

be given an opportunity to ask questions and will be given sufficient time to consider before consenting.

The subject's signed and dated informed consent to participate in the clinical trial must be obtained prior to any clinical trial related procedure being carried out in accordance with ICH GCP (4.8) and all applicable laws and regulations. The authorised person obtaining the informed consent must also sign the ICF.

Subjects must be re-consented to the most current version of the ICF(s) during their participation in the trial, if applicable.

A copy of the ICF(s) must be provided to the subject or the subject's legally authorised representative.

Subject card

At screening, subjects will be provided with a card stating that they are participating in a clinical trial and which contains contact address(es) and telephone number(s) of relevant trial site staff including the number for the investigator in case of emergency situations. The subject card also includes a local telephone number for the emergency unblinding CRO to be used if the investigator or delegated site staff cannot be reached or if unblinding in the IWRS cannot be performed.

